7.2 Baseline Definition

The data collected at the enrolment date will be considered as the baseline data for monitoring and evaluating the safety, tolerability, and acceptability of the investigating study product and other analyses unless it is specified. In some cases, the assessments at Week 5 prior to the first injection will be considered as the baseline.

8 DATA HANDLING/MANAGEMENT

All data will be collected and saved in CRF database and laboratory database. The details of data collection and data management are provided in Section 12 Data Management in SSP.

8.1 Premature Withdrawal and Missing Data

8.1.1 Premature Withdrawal

The reason(s) for withdrawal from the study must be recorded by the investigator in the CRF, including the participant's reason for withdrawn consent. Withdrawn participants will not be replaced. All available data from those who withdraw from the study earlier will be included in the analyses according to the study populations defined in Section 6. In the case that the study is prematurely discontinued, all available data will be used in the analyses that are still considered appropriate.

8.1.2 Methods for Missing Data

Missing data will occur when any requested data is not provided, leading to blank fields on the collection instrument. Answers such as "Not applicable" and "Not evaluable" are not considered to be missing data and should be displayed as such. Missing data will occur if the participants will miss visits and withdraw from the study prior to complete the study regimen.

8.2 Derived and Transformed Data

8.2.1 Age

The participants' date of birth or age will be recorded in CRF. If the age is not recorded in CRF, the age will be calculated based on the date of birth and the date of the completion of the CRF. In a case that the date of birth will be used in the calculation of the age, if the date of birth is partial missing, the missing month will be imputed by June; the missing day

will be imputed as the 30th; Otherwise, if the date of birth is missing completely, the date of birth will not be imputed and the age will be missing.

8.2.2 Changes from the Baseline

For the variables that the changes from the baseline will be evaluated in the analyses, the changes will be calculated by subtracting the baselines values of the variables from the values at post-baseline visits. If the baseline or the post-baseline value is missing, then the change from the baseline will be missing.

8.2.3 Corrected QT Intervals

The corrected QT interval measured by Bazett's (QTcB) or Fridericia's (QTcF) will be recorded in CRF.

9 STATISTICAL DATA ANALYSES

All data from enrolled participants will be analyzed according to the Analysis Populations described in Section 6.

9.1 Analysis Tools

Analyses for primary endpoints will be performed in SAS. All other descriptive and inferential statistical analyses will be performed using SAS and/or R statistical software.

9.2 Analysis Variables

The analysis variables consist of baseline participant characteristics, safety, tolerability, acceptability, sexual risk behavioral, and pharmacokinetics for primary, secondary, and exploratory analyses.

9.3 General Approach

When the use of descriptive statistics to summarize the study populations' characteristics is required, the following statistics will be used: for categorical variables, the number and percent in each category; for continuous variables, the mean, median, standard deviation, quartiles and range (minimum, maximum). When the use of a statistical test to assess the difference between two different time points within each the treatment arm is required, the following tests will be used: for categorical variables, McNemar test; for continuous variables the paired t-test or Wilcoxon signed-ranks test. When use of a statistical test to assess the differences between the two treatment arms is required, the following tests/models will be used: for binomial response variables, chi-square tests (Fisher Exact test will be used if there are cells with less than 5) or logistic regression models if other covariates need to be adjusted in the model; for continuous variables, t-test if the data are normal distributions) or nonparametric Wilcoxon rank sum test if data are not normally

distributed or linear regression models if other covariates need to be adjusted. Additional analyses will also be performed and described below.

To assess the adequacy of the randomization, participants in each of the two arms will be compared for baseline characteristics including demographics and laboratory measurements.

9.4 Baseline Characteristics

A table that includes the baseline characteristic variables of the enrolled participants will be presented. Summary statistics appropriate for the measurement scale will be used to describe the distribution of these variables. These summary statistics will be presented in tables by cohort and study arm among the enrolled participants in the oral phase and as well as among the participants that will be enrolled in the injection phase. Baseline characteristics will be compared between two study arms using chi-square test for categorical variables such as gender and using t-test or for continuous variables. The summary tables will be also stratified by US sites and Non-US sites to see whether these baseline measures differ by US sites vs international sites. The comparisons between the two treatment arms will be adjusted for sites (US vs. Non-US) if the differences are observed between US and Non-US sites.

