4.7 Randomization

Enrolled participants are randomized to one of two study arms with an active GSK1265744 to placebo ratio of 3:1 in two cohorts. The arm randomization is stratified by

gender and region (US and non-US sites) and done in blocks to ensure balanced treatment assignments within each gender and region (US and non-US). The randomization scheme is generated, operationalized and maintained by HPTN SDMC using Frontier Science & Technology Research Foundation, Inc. (FSTRF) system. Additional details regarding the process of randomization are included in the SSP Manual.

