9.5.5 Safety Endpoint

Primary safety endpoint is the proportion of participants experiencing any Grade 2 or higher clinical AEs or laboratory abnormalities since the initial injection to 12 weeks (8 weeks) after the last injection in Cohort 1 (Cohort 2) among the participants who complete at least one injection to evaluate the safety of the 744 injectable during the injection phase. A secondary safety endpoint is the proportion of Grade 2 or higher clinical AEs or laboratory abnormalities occurred from the initial injection to 76 weeks in both cohorts after last injection among the participants who complete at least one injection to evaluate the safety of the 744 injectable in long term; the proportion of Grade 2 or higher AEs or laboratory abnormalities occurred during the oral phase (Weeks 0-5) among all enrolled participants to evaluate the safety of the oral 744 product; and the proportion of Grade 2 or higher AEs or laboratory abnormalities occurred during the whole study period among the all enrolled participants to evaluate the safety of the oral and injectable product. The proportions of endpoints and the %95 confidence intervals will be estimated for each treatment arm. The 95% CIs will be estimated using Wilson score method¹. The proportions of endpoints will be compared between the treatment arms using Fisher Exact test.

In addition, the safety endpoint rate might be calculated for each treatment arm and compared between the treatment arms. The safety endpoint rate is the number of the participants who have experienced Grade 2 or higher clinical AEs or laboratory abnormalities during the study period (defined in each safety analysis) divided by the person-time-at-risk throughout the observation period within the study period.

The 95% exact confidence interval of the safety event rate will be calculated for each treatment arm, assuming the rate follows the Poisson distribution. The safety event rate will be compared between the treatment arms using exact Poisson test.

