9.6 Tolerability

To assess tolerability of 744 LA, the proportion (with 95% CI) of subjects who terminate from receiving injections prior to the full course due to AEs, intolerance of injection, frequency of injections, or burden of procedures related to injections out of those subjects that received at least one injection by cohort and treatment arm will be provided. The proportion will be compared between the treatment arms by cohort and in aggregate using Fisher Exact test.

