9.8 Study Medication Satisfaction Questionnaire

The Study Medication Satisfaction Questionnaire (SMSQ) will also be used to assess subject tolerability and satisfaction to the study medication in this trial. The SMSQ is a modified version of the current HIV Treatment Satisfaction Questionnaire (HIVTSQ) that does not include questions pertaining to treatment but rather study medication. The SMSQ is a 12-item self-reported scale that measures overall satisfaction with medication, general satisfaction/clinical, satisfaction with lifestyle/ease, and each individual satisfaction. This study uses the SMSQs (status version) and the SMSQc (change version).

The SMSQs will be administered at the following time points: Week 6, Week 18, and Week 30 in Cohort 1 and Weeks 6, 10, 18, 26, and 34 in Cohort 2. The SMSQc will be administered at Week 18 in Cohort 1 and Week 10 in Cohort 2.

For each question the responses will be summarized by the proportion of participants reporting the response on the Likert scale out of all those that answered the question at visit by the treatment arm. An overall treatment satisfaction score will be calculated for each participant at each visit. To evaluate the participants' experience of the medication with injection comparing to the experience of medication with tablets during the first 4 weeks of the study, the score derived from SMSQc will be summarized by treatment arm and compared between the treatment arms using t-test and using the linear regression model to adjust for site effect (US sites vs. Non-US sites). To evaluate the participants' experience of the medication with injection, the scores derived from SMSQs will be summarized by treatment arm and visit and compared between the treatment arms over time using GEE model to account for the correlations of the scores over time and will be evaluated the changes over time within the treatment arms. The analyses will be done by Cohort and in aggregate.

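### SAP 9.4 makes region adjustment of arm comparisons depend on undefined baseline differences, although region is a randomisation stratum and the rest of the SAP handles it inconsistently

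*SAP*

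**What the plan says.** SAP 4.7 stratifies the arm randomisation by "gender and region (US and non-US sites) and done in blocks to ensure balanced treatment assignments" within each stratum.

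SAP 9.4 splits the baseline tables by region "to see whether these baseline measures differ by US sites vs international sites". It then says that the comparisons between the two arms "will be adjusted for sites (US vs. Non-US) if the differences are observed between US and Non-US sites".

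For the primary safety endpoint, SAP 9.5.5 says: "The proportions of endpoints will be compared between the treatment arms using Fisher Exact test". For tolerability, SAP 9.6 says: "The proportion will be compared between the treatment arms by cohort and in aggregate using Fisher Exact test". Neither mentions a covariate. SAP 9.3 offers logistic or linear regression where covariates need adjusting, but does not say when that need arises.

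SAP 9.8 compares the SMSQc score between arms "using t-test and using the linear regression model to adjust for site effect", and SAP 9.9 does the same for the baseline acceptability questionnaire (BAQ).

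**The concern.** A covariate used to stratify randomisation belongs in the analysis because of the design, and because allowing for it recovers precision when the outcome depends on it. The rule in 9.4 looks instead at whether US and non-US participants differ in baseline measures. Regions may differ in race or weight while the outcome does not vary by region, or look alike at baseline while adverse-event reporting differs.

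The rule is also incomplete. It does not say which measures count, how large a difference must be, whether the decision is taken by cohort or overall, or which arm comparisons it governs. If it reaches the outcomes, two analyses of the primary endpoints could each be defended from the text. If it covers only the baseline tables, adjusting them informs no treatment comparison. What is at stake is undefined analytic discretion and some loss of power.

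**Working it through.** **1. How the SAP treats region, analysis by analysis**

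| Analysis | SAP section | Region |
|---|---|---|
| Arm comparisons, scope unstated | 9.4 | only if baseline differences are seen |
| Primary safety | 9.5.5 | none (Fisher) |
| Tolerability | 9.6 | none (Fisher) |
| PK models (active arm) | 9.7.1 | always |
| SMSQc | 9.8 | t-test and region-adjusted regression, unranked |
| SMSQs GEE | 9.8 | not named |
| BAQ | 9.9 | t-test and region-adjusted regression, unranked |
| FAQ GEE | 9.9 | not named |
| Sexual-behaviour GEE | 9.10 | not named (stratified by gender; age and race/ethnicity given as example covariates) |

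No single policy fits these rows. Gender, the other stratum, has no adjustment rule for the primary comparisons.

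**2. Continuous outcomes (illustrative)**

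Let R² be the share of outcome variance explained by region. The SAP gives no value; 0.1 and 0.2 are assumed. Under region-stratified allocation the true variance of the arm difference is (1 − R²) times what the unadjusted t-test estimates. Hence:

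- True size = 2 × [1 − Φ(1.96/√(1 − R²))]. At R² = 0.1: 1.96/0.949 = 2.07, size 0.039. At R² = 0.2: 1.96/0.894 = 2.19, size 0.028.
- Power, where the adjusted test has 80% = Φ(2.80 − 1.96/√(1 − R²)). At R² = 0.1: Φ(0.73) = 0.77. At R² = 0.2: Φ(0.61) = 0.73.

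**3. Binary outcomes (illustrative)**

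Inputs from the SAP: 3:1 allocation. 200 × 3/4 = 150 and 200 × 1/4 = 50, as in 4.1. 110 × 3/4 = 82.5 and 110 × 1/4 = 27.5, against 82 and 28 in 2.4.

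Assumed, because the SAP gives none of them: two equal regions, two-sided 0.05, the regional placebo event rates shown, and a common odds ratio (OR) of 1 or 3. There were 6000 simulated trials per scenario, and CMH is without continuity correction.

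| Size | Placebo rates by region | Measure | Fisher | Exact stratified | CMH |
|---|---|---|---|---|---|
| 82 vs 28 | 60% / 60% | type I error | 0.044 | 0.044 | 0.052 |
| 82 vs 28 | 60% / 60% | power, OR 3 | 0.60 | 0.60 | 0.64 |
| 82 vs 28 | 50% / 80% | type I error | 0.029 | 0.036 | 0.048 |
| 82 vs 28 | 50% / 80% | power, OR 3 | 0.50 | 0.52 | 0.57 |
| 82 vs 28 | 35% / 85% | type I error | 0.019 | 0.038 | 0.051 |
| 82 vs 28 | 35% / 85% | power, OR 3 | 0.41 | 0.49 | 0.54 |
| 150 vs 50 | 35% / 85% | power, OR 3 | 0.67 | 0.74 | 0.79 |

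The fair measure of stratifying is Fisher against the exact stratified test. Part of the further gain with CMH comes from leaving exact inference, since it also appears when the rates are equal. In the Cohort 1 scenarios with unequal rates, those two tests disagreed on significance in 0.7% to 7.8% of simulated trials.

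**4. What drives the result**

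The gain depends on how far outcome rates differ by region: nothing at 60%/60%, 0.49 − 0.41 = 0.08 in power at 35%/85%. The trigger in 9.4 inspects baseline measures by region and contains no information on that quantity.

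**The case against.** The strongest reply is about scope. The sentence stands in the baseline section, shortly after the statement that baseline characteristics are compared between arms, so it may govern those tables alone. On that reading the specific Fisher rules in 9.5.5 and 9.6 prevail and the harm is small. This stands as a possible reading, but the text does not settle it, and 9.3 provides a regression route that the trigger could activate.

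A second reply is that regional differences are very likely with sites in the US, Brazil and sub-Saharan Africa (4.6), so the rule would probably lead to adjustment anyway. That is plausible, but it argues for stating the adjustment outright.

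Several stronger readings are tempting and are not supported:

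- A reader might infer inflated type I error. The trigger looks at region against baseline, not at arm against outcome, and the unadjusted tests err on the conservative side.
- A reader might infer that the whole SAP adjusts for region only conditionally. Sections 9.7.1, 9.8 (SMSQc) and 9.9 (BAQ) adjust without condition.
- A reader might infer that the primary endpoints cannot be adjusted at all. A 2×2 Fisher test takes no covariate, but 9.3 names logistic regression; what is missing is a rule for when it applies.
- A reader might try to compute how often the trigger fires by chance. The SAP gives neither a list of measures nor a significance test for regional differences, and a false firing merely produces the adjustment that is wanted.
- A reader might object that 9.3 tests a null that is true by design: "To assess the adequacy of the randomization, participants in each of the two arms will be compared for baseline characteristics". That fits the randomised set. Section 9.4 also tabulates participants entering the injection phase, a set selected after randomisation, where an arm difference can be informative. Dropping baseline p-values is largely a reporting preference.

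**Conclusion.** The point holds as a defect of specification. The 9.4 rule has no criterion and no stated scope, and it tests something other than what decides whether region matters. The rest of the SAP does not supply a consistent policy: some analyses always include region, three sets of GEE models do not name it, two questionnaire scores have two unranked tests, and the primary Fisher tests are not protected from the trigger.

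The size is modest. The primary Fisher tests are valid as written. If outcomes do not vary by region, nothing material is lost. If they vary strongly, the assumed scenarios cost Fisher 0.02 to 0.08 in power at Cohort 1 size against an exact stratified test, and an unadjusted t-test falls from 80% to 77% or 73% power at an assumed R² of 0.1 or 0.2. These figures illustrate direction and scale and are not estimates for this trial. No figure stated in the SAP changes.

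**What to change.** - **9.4:** delete the conditional sentence.
- **9.3:** state that every model-based arm comparison includes region as a pre-specified covariate, and gender too where the analysis is not already stratified by it.
- **9.8, 9.9, 9.10:** add these terms to the SMSQs and FAQ GEE models, and add region to the sexual-behaviour GEE model, which is already stratified by gender.
- **9.8, 9.9:** name the region-adjusted regression as the primary test for the SMSQc and BAQ scores, with any t-test as supportive.
- **9.5.5, 9.6:** state that Fisher remains the test whatever the baseline tables show, and add a pre-specified sensitivity analysis stratified by the randomisation factors (exact stratified or CMH).
- **Optional:** present baseline by arm without p-values.

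The cost is SAP wording and slightly more programming. Both factors are already available from randomisation, and section 1 allows updates before the interim and final analyses. With four gender-by-region strata, the 28 placebo participants in Cohort 1 average 28/4 = 7 per stratum, which is why an exact stratified test or CMH is suggested for the sensitivity analysis.

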9.5 Safety Analysis

Safety data will be analyzed using the data from the safety populations described above respectively for each safety analysis. Safety will be analyzed by cohort and in aggregate.

9.5.1 Injection Site Reaction (ISR)

The number and percentage of participants experiencing each type of ISR sign or symptom will be tabulated by severity and treatment arm. For a given sign or symptom, each participant's ISR will be counted once under the maximum severity for all injection visits as well as by each successive injection. ISR other characteristics will be summarized by treatment arm and injection.

If a participant is observed with any inflammation symptom, the participant's temperature will be taken and reported in ISR CRF. The temperature will be graded according to the DAIDS Grading Table 2014 V2.0 and will be tabulated by study arm by each injection and compared between the two arms using Chi-square test.

9.5.2 AEs

AEs will be summarized using MedDRA system organ class and preferred terms. The number and percentage of participants experiencing each specific AE within a System Organ Class or within preferred term will be tabulated by severity or by relationship to study product within each treatment arm. For the calculations in these tables, a participant with multiple AEs within a category during the evaluating phase of the study will be counted once under the maximum severity or the strongest recorded causal relationship to study product. AEs will be summarized for those that will occur during the injection phase separately from those that will occur during the oral phase and as well as for those that will occur during the entire treatment phase of the study (the oral and the

injection phase). AEs leading to temporarily or permanently stopping drug will also be summarized by treatment arm.

A listing of EAEs reported to the DAIDS RSC Safety Office will provide details of the events including severity, relationship to study product, time between onset and last injection, number of injections received, and a summary of the event.

9.5.3 Local Laboratory Values

Scatter plots of some local laboratory values measured during the course of the study vs. the values at the baseline. If appropriate, horizontal/vertical lines representing boundaries for abnormal values will be plotted.

For each local laboratory measure, summary statistics will also be presented by treatment arm and visit time, as well as changes from baseline for post-enrollment values. Clinical laboratory abnormalities without an associated clinical diagnosis will also be reported as AEs and will be included in the tabulation of AEs described above.

In addition, the number (percentage) of participants with local laboratory values recorded as meeting Grade 1 AE criteria or above as specified in the DAIDS AE Grading Table (see Section 6.4.2 of the protocol) will be tabulated by treatment arm for each safety visit time point. In addition to SAEs, a list of the participants with the results: ALT \geq 3xULN and bilirubin \geq 2xULN will be provided.

9.5.4 Other Safety Measures

9.5.4.1 12-Lead ECG

The 12-lead electrocardiogram (ECG) findings will be summarized and listed by visit and treatment arm. Corrected QTc intervals will also be summarized by category for change from baseline: <30, \geq 30 to <60, and \geq 60 (described in table of ECG values of potential clinical importance below) by treatment group at each scheduled visit and for the maximum post baseline values. QTc interval is reported in CRF using one of the reporting methods, Bazett and Fridericia, and is denoted here by QTcB and QTcF, respectively.

Table 1. ECG Values of Potential Clinical Importance

ECG Parameter (QTcB/QTcF)	Potential Clinical Importance Range
Increase from baseline	<30
Increase from baseline	\geq 30 to <60
Increase from baseline	\geq 60

In addition, the number (percentage) of participants with ECG values recorded as meeting AE criteria will be tabulated by severity and the relationship to study product and compared between treatment arms using the method as described above.

9.5.4.2 Liver Events

Separate summaries will be presented for liver chemistry tests (AST, ALT, ALK PHOS, and bilirubin): Summary of maximum treatment emergent toxicities for oral phase, injection phase and oral+injection; Summary of changes in baseline toxicity to maximum toxicity for oral phase, injection phase and oral+injection.

By-subject listing of liver events and time of event relative to treatment will be produced. Box plots of liver chemistries (AST, ALT, ALP, and bilirubin) by treatment arm and visit. Scatter plots of maximum liver chemistries during oral (injection phase or oral+injection) phase vs. baseline. Matrix plot of maximum of liver chemistries on-treatment in oral, injection, or oral+injection phase will all be generated.

Kaplan-Meier plot of the time to first occurrence of grade 1 or greater elevation in ALT/AST will be generated by treatment arm during the oral, injection or oral+injection phase.

In addition, the number (percentage) of participants with liver chemistry values recorded as meeting AE criteria will be tabulated by severity and the relationship to study product and compared between the treatment arms as described above.

